## 6. INVESTIGATIONAL PLAN

### 6.1. Overall Study Design

[figure not shown]
This is a Phase 1b/2, open-label, multicenter study of DSP-7888 Dosing Emulsion in combination with checkpoint inhibitors (nivolumab or pembrolizumab) in adult patients with solid tumors, that consists of 2 parts: Phase 1b (a dose search part and an enrichment part) and Phase 2 dose expansion (Figure 2). In the Phase 1b part of this study there will be 2 arms: Arm 1 and Arm 2. In Arm 1, there will be 6 to 12 patients who will be dosed with DSP-7888 Dosing Emulsion and nivolumab and, in Arm 2, there will be 6 to 12 patients who will be dosed with DSP 7888 Dosing Emulsion and pembrolizumab.

In addition, a Phase 1b enrichment cohort of a further 10 patients, who have locally advanced or metastatic renal cell carcinoma (RCC) or urothelial cancer with primary or acquired resistance to previous checkpoint inhibitors, will be enrolled and will be dosed with DSP-7888 Dosing Emulsion and nivolumab, or DSP-7888 Dosing Emulsion and pembrolizumab, as per the investigator’s preference. The purpose of this Phase 1b enrichment cohort is to help evaluate the preliminary antitumor activity of DSP-7888 Dosing Emulsion at the safe dose level identified in the Phase 1b dose search part.

Once the recommended dose is determined in the Phase 1b dose search part, PROC patients will be enrolled in the Phase 2 part of the study with DSP-7888 Dosing Emulsion, exploring the combination with pembrolizumab. In Phase 2, a total of approximately 40 patients with PROC will be enrolled.

Objective disease assessments will be performed according to Table 7 (Phase 1b Arm 1), Table 8, (Phase 1b Arm 2), and Table 9 (Phase 2).

**Figure 2: Overall Study Design**

Note: The DSP-7888 Dosing Emulsion 3.5 mg + a PD-1 inhibitor cohort will only open if >1 out of 6 patients from the DSP-7888 Dosing Emulsion 10.5 mg + a PD-1 inhibitor cohort report a DLT.

### 6.1.1. Phase 1b

#### 6.1.2. Dose Search Part

After providing written informed consent, patients will undergo screening assessments, which will include a careful review of each patient's medical history.

Patients will be administered doses of DSP-7888 Dosing Emulsion intradermally in both arms of the study (Arm 1 and Arm 2). Arm 1 will include patients with indications approved by the Health Authorities for treatment with nivolumab: advanced melanoma, non-small cell lung cancer (NSCLC), RCC, urothelial carcinoma, head and neck squamous cell carcinoma (HNSCC), hepatocellular carcinoma (HCC), and microsatellite instability-high or mismatch repair-deficient (MSI H/dMMR) colorectal cancer. Arm 2 will include patients with indications approved by the Health Authorities for treatment with pembrolizumab: melanoma, NSCLC, HNSCC, urothelial carcinoma, MSI-H/dMMR cancer, gastric cancer or gastroesophageal junction adenocarcinoma, and cervical cancer (Figure 3).

In the Phase 1b dose search part of the study, during the Arm 1 induction phase (4 weeks), DSP-7888 Dosing Emulsion will be administered once weekly for 4 weeks, with nivolumab administered every other week. In the subsequent Arm 1 maintenance phase, DSP-7888 Dosing Emulsion will be administered once every 2 weeks with nivolumab until a discontinuation criterion is met. Arm 2 will include patients with indications approved by the Health Authorities for treatment with pembrolizumab: melanoma, NSCLC, HNSCC, urothelial carcinoma, MSIH/-dMMR cancer, gastric cancer or gastroesophageal junction adenocarcinoma, and cervical cancer. During the Arm 2 induction phase (6 weeks), DSP-7888 Dosing Emulsion will be administered once weekly for 6 weeks, with pembrolizumab administered once every 3 weeks. In the subsequent Arm 2 maintenance phase, DSP 7888 Dosing Emulsion will be administered once every 3 weeks with pembrolizumab until a discontinuation criterion is met.

Both programmed cell death-1 (PD-1) inhibitors (nivolumab and pembrolizumab) will be administered in the approved dose and schedule starting on Day 1 of the study. Study sites will not be limited to any arm of the study, and each arm will investigate the recommended dose in parallel.

**The Phase 1b dose search part of the study is completed, and no further patients will be enrolled under the dosing regimen described above (this legacy regimen is also depicted in Appendix 8). For patients enrolled under the Phase 1b enrichment part of the study, the dosing regimen described below will be followed per Amendment 5 of the protocol.**

#### 6.1.3. Enrichment Part

The Phase 1b enrichment cohort (consisting of the additional 10 patients) will include patients with locally advanced or metastatic RCC or urothelial carcinoma who experienced disease progression per iRECIST (immune confirmed progressive disease [iCPD]) during or within 3 months of last dose of the most recent prior anti-PD-1/PD-L1-based treatment.

Patients will be treated with the combination of DSP-7888 Dosing Emulsion and nivolumab, or DSP 7888 Dosing Emulsion and pembrolizumab, as per the treating physician's choice.

The administration of DSP-7888 Dosing Emulsion and anti-PD1 therapy in the Phase 1b enrichment cohort will differ from that in the Phase 1b dose search part of the study, and will be staggered as follows:

Arm 1 (Enrichment Cohort Only): DSP-7888 + nivolumab combination:

- DSP-7888 Dosing Emulsion will start on Day 1, Q1W for first 4 weeks, then Q2W thereafter
- Nivolumab will start on Day 1 of Cycle 3 (Day 29), Q2W

Arm 2 (Enrichment Cohort Only): DSP-7888 + pembrolizumab combination:

- DSP-7888 Dosing Emulsion will start on Day 1, Q1W for first 3 weeks, then Q3W thereafter
- Pembrolizumab will start on Day 1 of Cycle 2 (Day 22), Q3W

#### 6.1.4. Phase 2

A Phase 2, multicenter, open-label, single-arm, study will be conducted to evaluate the efficacy and safety of DSP-7888 Dosing Emulsion in combination with pembrolizumab in patients with advanced high-grade serous epithelial ovarian, fallopian tube, or primary peritoneal cancer who were previously treated with platinum-based therapy and experienced resistance to platinum-based therapy, defined as patient relapsed within 6 months after last dose of platinum-based therapy. Patients must have received 1 to 4 previous treatment regimens.

The Phase 2 dose of DSP-7888 Dosing Emulsion will be the recommended dose as determined in the Phase 1b Arm 2 part of the study.

Approximately 40 eligible PROC patients are expected to be enrolled in the Phase 2 dose expansion part of the study.

For patients enrolled under Protocol Amendment 4, the administration of DSP-7888 Dosing Emulsion and anti-PD1 in the Phase 2 dose expansion cohort is the same as that in the Phase 1b Arm 2 of the dose search part. For patients enrolled under Protocol Amendment 5, administration of DSP-7888 Dosing Emulsion and anti-PD1 will be staggered as follows:

DSP-7888 + pembrolizumab combination:

- DSP-7888 Dosing Emulsion will start on Day 1, Q1W for first 3 weeks, then Q3W thereafter
- Pembrolizumab will start on Day 1 of Cycle 2 (Day 22), Q3W

##### 6.1.4.1. Duration of Treatment

The study consists of 4 periods: Prescreening period, Screening period, Treatment period, and Follow-up period (See [Appendix 7](#)).

Each patient will participate in the trial from the time the patient signs the Prescreening informed consent form (ICF) until completion of survival follow-up (see [Figure 2](#)).

Human leukocyte antigen (HLA)-eligible patients in the Prescreening period will move on to a Screening period within a 28-day window from Cycle 1 Day1. Following Screening, all eligible

patients will receive treatment of DSP-7888 Dosing Emulsion in combination with pembrolizumab or nivolumab, dependent upon phase of the study.

For those patients enrolled under Protocol Amendment 5, DSP-7888 Dosing Emulsion will start on Day 1, pembrolizumab will start on Day 1 of Cycle 2 (Day 22), and then once every 3 weeks thereafter until the patient completes 35 cycles (approximately 24 months) of study treatment (if the patient is experiencing clinical benefit, and in the opinion of the investigator it is in the patient's best interest to continue the study beyond 35 cycles, the patient may continue treatment after documented discussion with the Sponsor). Reasons for treatment discontinuation are described in [Section 7.3.1](#).

Once patients discontinue or complete treatment, they will enter the follow-up period including disease assessment follow-up for any patient who discontinues study treatment for a reason other than immune confirmed PD (iCPD), and/or survival follow-up.

#### **6.1.4.2. Prescreening Period**

After signing the HLA screening ICF, patients will be evaluated for HLA subtype eligibility. Blood samples must be submitted to a centralized laboratory for HLA testing to determine patient eligibility for enrollment into the study. Patients found to be HLA eligible will move on to participate in further screening assessments for the complete evaluation of all other study eligibility criteria. Patients may proceed with the HLA screening ICF and HLA test while still receiving the prior therapy.

#### **6.1.4.3. Screening Period**

A Screening period will start once the patient signs the main ICF, and all procedures should be completed within 28 days from Cycle 1 Day 1. In the Screening period, patient eligibility will be determined based on the eligibility criteria, and patients will undergo screening assessments according to the Schedule of Assessments (SOA). Tissue samples (fresh or archival) will be required for exploratory biomarker analysis. Post-treatment biopsies are requested per SOA, unless collecting the tumor biopsy is determined to be not medically feasible by the treating investigator.

#### **6.1.4.4. Treatment Period**

Per Amendment 5, the treatment period consists of 2 treatment phases: Induction phase and Maintenance phase.

1. Induction phase (First cycle)
  - DSP-7888 Dosing Emulsion 10.5 mg intradermal injection, once weekly (Q1W), Days 1, 8, and 15 of Cycle 1
2. Maintenance phase (All cycles after Cycle 1 up to Cycle 35)
  - DSP-7888 Dosing Emulsion 10.5 mg intradermal injection, Day 1 of Cycle 2 (Q3W) and each subsequent cycle
  - Pembrolizumab 200 mg IV infusion Day 1 of Cycle 2 (Q3W) and each subsequent cycle until discontinuation or up to Cycle 35

On the days when both DSP-7888 Dosing Emulsion and pembrolizumab are administered, DSP-7888 Dosing Emulsion should be administered first. Study treatment may be modified for AEs per dose modification guidelines or based on the clinical judgment of the treating investigator.

Patients will be asked to undergo study specific visits and procedures according to SOA. Patients will be evaluated for objective response to study drug treatment with radiographic imaging (computer tomography [CT] scan or magnetic resonance imaging [MRI]) using RECIST (v.1.1) every 6 weeks for 24 weeks, and then every 12 weeks until progression. If a patient experiences objective disease progression according to RECIST (v 1.1) and is clinically stable, the patient will continue on treatment with study drug until the patient experiences iCPD per iRECIST.

Clinical stability is defined as:

- No worsening of performance status
- No clinically relevant increase in disease-related symptoms
- No requirement for intensified management of disease-related symptoms (such as analgesics, radiation, or palliative care)

Patients who remain on study treatment following objective disease progression per RECIST (v.1.1) will continue to be evaluated for objective response to study treatment according to the SOA and to iRECIST.

Patients also will be monitored for serum CA-125 using GCIG CA-125 criteria as part of clinical evaluation of response according to the SOA. Progressive disease may not be determined by CA-125 progression alone.

Adverse event monitoring will be ongoing throughout the study and graded in severity according to the guidelines outlined in the National Cancer Institute (NCI) CTCAE version 4.03. Patients will be evaluated for AEs from the time of signing the main ICF until 30 days after their last dose of study treatment.

Blood samples will be required for safety labs, CA-125 assessment, as well as the biomarker assay during the treatment period, and a fresh tumor tissue sample is requested post-treatment for biomarker assessment if medically feasible.

#### **6.1.4.5. Follow-up Period**

The follow-up period will begin once a patient has discontinued study treatment. Follow-up period includes disease assessment follow-up (for patients who discontinue study treatment for a reason other than iCPD per iRECIST) and survival follow-up.

Patients who discontinue study treatment without experiencing iCPD will continue to undergo tumor assessment and evaluation of CA-125 (Phase 2), according to the SOA until up to 24 months after last dose of study drug, the start of new anticancer therapy, iCPD per iRECIST, death, loss to follow-up, withdrawal of consent, or the end of the study, whichever occurs first.

Patients who discontinue study treatment when experiencing iCPD per iRECIST with study drug, or patients who discontinue study treatment without experiencing iCPD per iRECIST, but who experience iCPD per iRECIST or start new anticancer therapy during disease follow-up will be assessed for survival and new anticancer treatment status per the SOA, until up to 24 months

after the last dose of study drug, death, withdrawal of consent, loss to follow-up, or end of the study, whichever occurs first.

[figure not shown]
The safety and tolerability of DSP-7888 Dosing Emulsion in combination with immunotherapy PD-1 inhibitors will be assessed for the duration of study treatment and follow-up (see [Table 7](#), [Table 8](#), and [Table 9](#) for the respective SOAs).

All AEs will be collected and recorded for each patient from the date of signing the main ICF for the study until 30 days after last study drug administration. Any pregnancies that occur within 180 days after last study drug administration are to be captured. An AE will be followed until it is either resolved, has returned to baseline, or is determined to be a stable or chronic condition (see [Table 7](#), [Table 8](#), and [Table 9](#)).

[figure not shown]
Particular attention should be given to the follow up of any **Grade 3 or higher** injection site reactions ongoing at the End of Treatment period until resolution, return to baseline, determined to be a stable or chronic condition or until the patient is lost to follow up or the patient has died. Please record the data within EDC per eCRF instructions. In the instance of resolution with sequelae, please be sure to enter the sequelae as a separate AE (eg skin discoloration, persistent induration, scarring “from ISR”). To facilitate this careful follow up, please consider use of video teleconference with the patient during the follow up period post study.

Objective disease assessments will be performed according to RECIST and iRECIST. For Phase 1b, the first assessment will be performed during Cycle 3, at 4 weeks for the nivolumab arm and at 6 weeks for the pembrolizumab arm, and at Weeks 12, 18, and 24, after the first dose of DSP-7888 Dosing Emulsion. After that, objective disease assessments will occur every 12 weeks until patient discontinuation from the study. For Phase 2, patients will be evaluated for objective response to study drug treatment with radiographic imaging every 6 weeks for 24 weeks and then every 12 weeks until progression.

**Figure 3: Schematic of Study Arm 1 and Study Arm 2 in Phase 1b**

**Figure 4: Schematic of Phase 2 of Study**

## 6.2. Planned Number of Patients

In Phase 1b of the study, there will be approximately 6 to 12 patients for each arm, up to a total of up to 24 patients. In the enrichment cohort, 10 patients will be enrolled. If anti-tumor activities are observed in any tumor type, additional patients may be enrolled for further assessment. In Phase 2 of the study, approximately 40 patients will be enrolled. Additional patients may be enrolled to further assess anti-tumor activities in the subgroups of interest. However, the total sample size of Phase 2 cannot exceed 60 patients.

## 6.3. Treatment Assignment

### 6.3.1. Phase 1b

The administration of DSP-7888 Dosing Emulsion and anti-PD1 therapy in the Phase 1b enrichment cohort will be staggered as follows:

Arm 1 (Enrichment Cohort Only): DSP-7888 + nivolumab combination:

- DSP-7888 Dosing Emulsion 10.5 mg will start on Day 1, Q1W for first 4 weeks, then Q2W thereafter
- Nivolumab 240 mg will start on Day 1 of Cycle 3 (Day 29), Q2W

Arm 2 (Enrichment Cohort Only): DSP-7888 + pembrolizumab combination:

- DSP-7888 Dosing Emulsion 10.5 mg will start on Day 1, Q1W for first 3 weeks, then Q3W thereafter
- Pembrolizumab 200 mg will start on Day 1 of Cycle 2 (Day 22), Q3W

Patients in this study will receive DSP-7888 Dosing Emulsion at assigned dose levels, according to [Table 4](#) and [Table 6](#) and according to the study arm. Each study arm will begin at Dose Level I, and dose de-escalation will proceed independently of the other arms if a safety concern occurs in Dose Level I. For a given patient, the appropriate PD-1 combination partner will be determined by the treating investigator (see [Table 5](#)) for dose schedule. Dose adjustments of DSP-7888 Dosing Emulsion are allowed as per protocol. As per their labels and package inserts, dose adjustments for nivolumab and pembrolizumab are not recommended.

The Phase 1b enrichment cohort (10 patients) will be treated with the combination of DSP-7888 Dosing Emulsion and nivolumab, or DSP-7888 Dosing Emulsion and pembrolizumab, as per the treating physician's choice, following the dosing guidelines and schedule stated above in this section.

For an individual patient, the combined treatment of DSP-7888 Dosing Emulsion and nivolumab or DSP-7888 Dosing Emulsion and pembrolizumab will continue until the investigator determines that the patient is no longer likely to receive clinical benefit from DSP-7888 Dosing Emulsion. However, to assess the benefit of radiologic imaging in accordance with the iRECIST criteria, in cases of suspected progression, the protocol requires a confirmatory scan performed 4 to 8 weeks following the initial scan that shows the suspected progression.

Patients will continue to receive study treatment independent of radiologic assessment or progression:

1. Provided that the investigator considers it to be safe for the patient
2. Provided that the investigator determines that there is potential benefit for the patient
3. When the patient is willing to continue

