**Duration of treatment:**

Patients will have access to study treatment as long as they are benefiting from study treatment in Phase 1b.

For Phase 2 of the study, patients will have access to study treatment as long as they are benefiting from study treatment or have received up to a total of 35 treatment cycles (approximately 105 weeks). Patients may continue the study treatment beyond 35 treatment cycles if patients are experiencing clinical benefit after documented discussion with the Sponsor.

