## 7.3. Withdrawal Criteria

### 7.3.1. Reasons for Discontinuation of Protocol Therapy

Patients have the right to withdraw fully or partially from the study at any time and for any reason without prejudice to their future medical care by the physician or at the institution.

Withdrawal of partial consent means that the patient does not wish to take investigational product any longer but is still willing to collaborate in providing further data by continuing on the study (eg, participate in all subsequent study visits or procedures). Patients may decline to continue receiving investigational product at any time during the study. These patients, as well as those who have stopped receiving investigational product for other reasons (eg, investigator or Sponsor concern) should continue the schedule of study observations. The patients may withdraw consent for continued treatment and still provide consent to be followed up in the follow-up period.

Patients will be discontinued from protocol therapy for any of the following reasons:

- Patients completes 35 cycles (approximately 105 weeks) of study treatment (Phase 2 part only)

Note: if the patient is experiencing clinical benefit, and if, in the opinion of the investigator, it is in the patient's best interest to continue the study beyond 35 cycles, the patient may continue treatment, after documented discussion with the Sponsor

- Documented disease progression (see [Appendix 2](#))
- The need for a prohibited treatment for a concomitant illness or AE
- An AE that precludes further administration of DSP-7888 Dosing Emulsion (see [Section 8.3.1](#) and [Section 8.3.2](#))
- Patient withdraws consent for continued administration of DSP-7888 Dosing Emulsion, nivolumab, or pembrolizumab

Note: if a patient withdraws consent from study treatment, the patient may maintain his/her consent to participate in the follow-up portion of the study

- The investigator believes it is in the patient's best interest to discontinue protocol treatment or to initiate alternative treatment
- Pregnancy
- Lost to follow-up (3 attempts to contact the patient must be made by the investigative site by phone or email before a patient is considered lost to follow-up)
- Patient moves out of the investigator's catchment area or is unable to continue to come to the investigational site
- At Sponsor's request

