### **11.2. Assessment of Efficacy**

Tumor response will be determined by the investigator according to RECIST v1.1 and iRECIST. Tumor response according to iRECIST will be used for treatment decision-making and other supporting disease-specific efficacy measurements. Tumor evaluations during treatment period in Arm 1 will be performed at Weeks 4, 12, 18, and 24, followed by every 12 weeks until disease progression. Tumor evaluations during treatment period in Arm 2 will be at Weeks 6, 12, 18, and 24, followed by every 12 weeks until disease progression.

Tumor evaluations during the treatment period in Phase 2 will be at Weeks 6, 12, 18, and 24, followed by every 12 weeks until disease progression or the completion of 35 treatment cycles. Patients who discontinue study treatment without experiencing iCPD will continue to undergo tumor assessment according to the SOA until up to 24 months after the last dose of study drug, the start of new anticancer therapy, iCPD per iRECIST, death, loss to follow-up, withdrawal of consent, or the end of the study, whichever occurs first.

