### **Treatment decision**

If a patient experiences objective disease progression according to RECIST (v 1.1) and is clinically stable, patients will continue on treatment with study drug until patients experience immune confirmed PD (iCPD) per iRECIST.

Clinical Stability is defined as:

- No worsening of performance status
- No clinically relevant increase in disease-related symptoms
- No requirement for intensified management of disease-related symptoms (such as analgesics, radiation, or palliative care)

Patients who remain on study treatment following objective disease progression per RECIST (v.1.1) will continue to be evaluated for objective response to study treatment according to the SOA and evaluated according to iRECIST

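### SAP 3.3 gives no arm to a Phase 1b patient who stops before the first PD-1 dose; separately, Protocol 6.3.1 and 7.3.1 conflict on stopping Phase 1b treatment at progression

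*Protocol*

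**What the plan says.** **Arm membership.** SAP 3.3 defines Arm 1 as Phase 1b patients who received one or more doses of DSP-7888 and nivolumab, and Arm 2 likewise with pembrolizumab. SAP 3.1 admits anyone who received any study drug to the Full Analysis Set and classifies by treatment assigned. SAP 3.2 admits the same patients to the Safety Set and classifies by treatment received. If the assigned treatment was never given, it falls back on whichever treatment came first. SAP 5.2.1 and 5.4.1 present Phase 1b disposition and adverse events by arm. SAP 5 makes safety the focus of the final report and drops the efficacy analysis.

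**Stopping at progression, Phase 1b.** Protocol 6.3.1 says combined treatment "will continue until the investigator determines that the patient is no longer likely to receive clinical benefit from DSP-7888 Dosing Emulsion". It then requires "a confirmatory scan performed 4 to 8 weeks following the initial scan that shows the suspected progression", and adds: "Patients will continue to receive study treatment independent of radiologic assessment or progression", provided treatment is considered safe and potentially beneficial and the patient is willing. The synopsis agrees: "Patients will have access to study treatment as long as they are benefiting from study treatment in Phase 1b".

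Protocol 7.3.1 lists reasons for which patients will be taken off protocol therapy. One is "Documented disease progression", with a pointer to Appendix 2. Only the 35-cycle bullet in that list is restricted to Phase 2. Appendix 2, which is restricted to no phase, says that after RECIST 1.1 progression in a clinically stable patient, "patients will continue on treatment with study drug until patients experience immune confirmed PD (iCPD) per iRECIST".

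**The concern.** The arm rule fits the dose-search schedule, where both drugs start on Day 1. It does not fit the enrichment schedule, which opens with three or four weeks of DSP-7888 alone. Patients who leave in that period, because of an adverse event, withdrawal or early progression, are the ones an arm-level safety table should not lose. They would still count in an overall Phase 1b column, so the arm columns would not add up to it.

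The progression texts raise a different question. Two sections give different instructions for the same Phase 1b patient, and neither yields to the other. Time on treatment feeds exposure and the adverse-event window, which SAP 5.4.1 runs to 30 days after the last dose. Adverse-event incidence and dose intensity are Phase 1b primary endpoints. Protocol 12.1 also requires patient-management deviations to be identified and closed before database lock. Treating past iCPD is compliant under one section and a deviation under the other.

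**Working it through.** **Step 1. The DSP-7888-only period (Protocol 6.3.1; SAP Figure 1).**
- Arm 1 enrichment: DSP-7888 on Days 1, 8, 15 and 22, first nivolumab on Day 29. That is 4 doses (4 × 10.5 = 42 mg) before any PD-1 inhibitor.
- Arm 2 enrichment: DSP-7888 on Days 1, 8 and 15, first pembrolizumab on Day 22. That is 3 doses (3 × 10.5 = 31.5 mg).
- Dose search: both drugs on Day 1, so there is no such period.

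**Step 2. Apply the SAP to an enrichment patient who stops within that period.**
- 3.1: in the Full Analysis Set, by assigned treatment.
- 3.2: in the Safety Set. The fallback returns DSP-7888, which both arms share. DSP-7888 is due on Days 1, 8, 15 and 22 in both enrichment schedules, so the doses given do not identify the arm either.
- 3.3: the condition of both drugs is not met, so the patient is in neither arm.

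The reason for stopping plays no part, so the gap exists whichever progression rule governs.

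**Step 3. Set the progression texts side by side.**

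| Phase 1b patient | 6.3.1 and synopsis | 7.3.1 with Appendix 2 |
|---|---|---|
| RECIST 1.1 progression, clinically stable | May continue | Continues until iCPD |
| RECIST 1.1 progression, not clinically stable | May continue if judged safe and potentially beneficial | Stops (inferred: Appendix 2 exempts only stable patients) |
| iCPD | May continue on the same conditions | Stops |

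Other text does not decide between them. Section 11.2 says "Tumor response according to iRECIST will be used for treatment decision-making", and 6.1.2 runs dose-search maintenance "until a discontinuation criterion is met". Both lean towards 7.3.1, but neither mentions 6.3.1.

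**Step 4. Can an iCPD stop change the arm?** Inputs: first scan at Week 4 (Arm 1) or Week 6 (Arm 2), from Tables 7 and 8; confirmation 28 to 56 days later, from Appendix 3; visit window ±2 days, assumed to apply to scans.

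Earliest iCPD = (first scan day − 2) + 28. Latest first PD-1 dose = nominal day + 2.

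| Schedule | Latest first PD-1 dose | Earliest iCPD | Gap (days) |
|---|---|---|---|
| Arm 1 enrichment | 29 + 2 = 31 | 27 + 28 = 55 | 24 |
| Arm 2 enrichment | 22 + 2 = 24 | 41 + 28 = 69 | 45 |
| Arm 1 dose search | 1 + 2 = 3 | 27 + 28 = 55 | 52 |
| Arm 2 dose search | 1 + 2 = 3 | 41 + 28 = 69 | 66 |

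On schedule it cannot.

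**Step 5. Exposure when the rules part at iCPD (earliest progression, enrichment, scan before that day's dosing).**
- Arm 1: confirmation on Day 29 + 28 = 57 to 29 + 56 = 85. Nivolumab already given: Days 29 and 43 (2 doses), up to Days 29, 43, 57 and 71 (4 doses).
- Arm 2: confirmation on Day 43 + 28 = 71 to 43 + 56 = 99. Pembrolizumab already given: Days 22, 43 and 64 (3 doses), up to Day 85 as well (4 doses).

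Later progression means more doses.

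**The case against.** On arm membership, the SAP already classifies the Full Analysis Set by assignment, and SAP 5.2.1 presents end-of-treatment reasons by treatment assignment. A programmer could reasonably carry that over, and the patients would still appear in listings. This lowers the risk without removing it. The safety tables use the Safety Set, whose fallback names no arm, and 3.3 is the only text that defines the arms.

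On progression, there are two reconciling readings. Section 6.3.1 and the synopsis sentence are written for Phase 1b and could be taken to override a general list. Alternatively, the 6.3.1 sentence comes straight after the confirmatory-scan requirement, so a site could take it to cover only unconfirmed progression; for clinically stable patients the sections would then agree. Each reading is tenable, but they lead to different conduct after iCPD and the protocol does not choose. What stands is that the fault is a missing cross-reference.

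A reader might join the two issues and infer that an iCPD stop decides the SAP arm. Step 4 rules that out on schedule. The one on-schedule link is narrow: an Arm 1 enrichment patient with progression at Week 4 who is not clinically stable. The scan and the first nivolumab dose share nominal Day 29. Table 7 puts tests before injection but does not require the scan to be read by then. Such a patient might also be stopped under 6.3.1.

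A reader might also try to put a percentage on the distortion of arm-level event rates. The documents give neither the number of patients who stop before the first PD-1 dose nor the arm split of the 10 planned enrichment patients, so any such figure would be illustrative only.

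**Conclusion.** Both parts hold, and they are separate.

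The SAP gap is the more useful to close. As written, a Phase 1b patient who received DSP-7888 only belongs to neither arm, in a report whose main content is safety. Exposure to the gap is limited to the staggered schedule: the four weeks before Day 29 in Arm 1 and the three weeks before Day 22 in Arm 2. The number affected is unknown and may be zero.

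The protocol conflict is real but modest. It concerns how long Phase 1b patients are treated after progression, and what counts as a deviation. At the earliest progression, the rules part at iCPD after 2 to 4 nivolumab doses or 3 to 4 pembrolizumab doses. For patients who are not clinically stable they part sooner, a step that rests on inference from Appendix 2.

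DLT-based dose selection and RECIST response are not affected. Neither is Phase 2, where 6.1.4.4 matches Appendix 2.

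**What to change.** **SAP 3.3.** Add: *A Phase 1b patient who received DSP-7888 only is classified in the arm of the assigned PD-1 inhibitor.* Flag these patients in the listings. This assumes the assigned inhibitor is recorded at entry, which is plausible because the two arms follow different visit schedules. The cost is one sentence and a flag. The small downside is that arm-level rates then include patients never exposed to the PD-1 inhibitor.

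**Protocol 7.3.1 or 6.3.1.** Because 6.3.1 and the synopsis sentence are the Phase 1b-specific texts, add *Phase 1b: see 6.3.1* to the progression bullet in 7.3.1. If the sponsor intends the iCPD stop, instead limit the 6.3.1 sentence with *until iCPD*. Either edit is a protocol amendment and needs IRB/IEC re-approval under 15.1, so bundle it with the next amendment rather than issuing one for this alone.
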